5.1 Treatment Adherence

Treatment will be administered in four-weekly supply as per the PBS. The time and date of first study dose will be recorded. Treatment adherence will be monitored by self-report.

5.2 Prior and Concomitant Medications

The use of concomitant medications prior to, during, and post-treatment must be in line with the product information for glecaprevir/pibrentasvir or sofosbuvir/velpatasvir. The treating clinician should thoroughly review the participants medical history and review all medications the patient is taking prior to treatment and commences taking during treatment for potential drug-drug interactions (https://www.hep-druginteractions.org/).

6. Study procedures

6.1 Visits and Procedures

The following assessments must be conducted at study visits as per the Schedule of Assessments:

Anti-HCV Ab (POC)	SD Bioline HCV point-of-care assay
APRI	AST to platelet ratio
HCV RNA (POC)	Xpert [®] HCV Viral Load Fingerstick point-of-care assay
DBS	Dried Blood Spot research sample collection
Behavioural questionnaire	Behavioural survey (screening or follow-up version as applicable)
Health outcomes survey	EQ-5D-5L
Treatment adherence	Adherence questionnaire
HCV RNA (SOC) ^a	Quantitative HCV RNA via local laboratory (baseline only)
HCV genotype (SOC) ^a	HCV genotype via local laboratory (baseline only)
Liver function tests ^a	ALT, AST, GGT, total bilirubin, albumin, alkaline phosphatase (baseline only)
Biochemistry ^a	Creatinine, sodium, chloride, potassium (baseline only)
Full blood count ^a	Haemoglobin, white blood cells, platelets, neutrophils (baseline only)
HIV serology (POC)	HIV Ab (screening only)
HBV serology (POC)	Hepatitis B surface antigen (HepBsAg) (screening only)
FibroScan®	Transient elastography
Pregnancy test	For women of childbearing potential, a negative urine (or serum) βHCG test at baseline

^a Only when clinically indicated

The following assessments and procedures must be performed at each visit as specified below.

Screening visit (All participants)

- Informed consent
- HCV risk assessment (Figure 2)
 - Reported risk for HCV infection
 - i. Known current or past HCV infection (self-report)
 - ii. Risk behaviour for HCV transmission: History of injecting drug use, history of incarceration, receipt of opioid substitution therapy (self-report)

• No reported risk for HCV infection

- Point-of-care HCV testing
 - o Point-of-care anti-HCV antibody (*no reported risk for HCV infection*)
 - AND/OR
 - Point-of-care HCV RNA (*reported risk for HCV infection or positive point-of-care anti-HCV Ab*)
- Non-invasive liver disease assessment (Fibroscan[®] or APRI)
 - Fibroscan[®] will be performed in preference to APRI if available.

Participants will be notified of their point-of-care anti-HCV Ab and/or HCV RNA results on the same-day (where possible).

Participants who are anti-HCV Ab negative and report no risk factors for HCV acquisition will complete the above screening procedures but will not be followed longitudinally.

Participants with *current HCV infection* (HCV RNA positive) and/or participants who report being *at risk of HCV infection* (HCV RNA negative; history of injecting drug use, history of incarceration, receipt of opioid substitution therapy with 12 months of screening) will undergo the following assessments:

- Point-of-care HCV RNA (if not performed previously)
- Point-of-care HIV and HBV serology
- Collection of dried blood spot (DBS) sample (research sample)
- Screening behavioural questionnaire
- Health outcomes survey (EQ-5D-5L)
- Education regarding HCV transmission and risk reduction

Baseline visit (Point-of-care HCV RNA positive participants only)

Assessment for DAA initiation

This can, and should (if possible), be conducted on the day of the screening (or follow up) visit.

• Clinical assessment with a study nurse

If clinically indicated, the following standard-of-care blood tests will be collected:

- o Phlebotomy for liver function tests, full blood count, biochemistry
- o HCV genotyping via local laboratory
- o HCV RNA (quantitative or qualitative) via local laboratory
- Pregnancy test (for women of childbearing potential only)
- Initiation of pan-genotypic DAA therapy (glecaprevir/pibrentasvir or sofosbuvir/velpatasvir) following discussion with an experienced clinician (face-to-face or remote), if appropriate

Point-of-care HCV RNA positive participants assessed as suitable and willing for treatment will be prescribed eight weeks glevaprevir/pibrentasvir or 12 weeks sofosbuvir/velpatasvir under PBS S85 (dispensed as a 4-week supply). The time of the first dose of therapy will be recorded.

Participants not deemed suitable for treatment under this simplified community-based model of care will be referred for specialist follow-up.

For point-of-care HCV RNA positive participants who decline DAA treatment, site study staff will discuss with the participant the reasons for not initiating DAA treatment. These participants may remain in the cohort and will be followed longitudinally. They will also be approached for involvement in the qualitative study.

On-Treatment and Post-Treatment Phase (For participants who initiate DAA treatment)

On-Treatment Week 4 and Week 8

The following procedures will occur at Week 4 and Week 8 on-treatment:

- Clinical assessment with nurse (as required)
 - Clinical assessment will be conducted on an as-needed basis at discretion of the participant and/or the nurse.
- Participants will receive a 4-week supply of DAA therapy (glecaprevir/pibrenatasvir or sofosbuvir/velpatasvir), as appropriate
- Treatment adherence questionnaire

End of Treatment (EOT)

Participants will return at end of treatment for the following:

- Clinical assessment with nurse
- POC HCV RNA
- DBS (research sample collection)
- Treatment adherence questionnaire
- Follow-up behavioural questionnaire
- Health outcomes survey (EQ-5D-5L)

Post-treatment week 12 (PTW12)

Participants will return 12-weeks post EOT for the following:

- Clinical assessment with a nurse
- POC HCV RNA
- DBS (research sample collection)
- Follow-up behavioural questionnaire
- Health outcomes survey (EQ-5D-5L)

Follow Up Phase (All participants)

Follow up 1, 2, 3, 4, 5, 6

Participants with or at risk of HCV infection will return every 6 months enrolment for the following:

- POC HCV RNA
- DBS (research sample collection)
- Follow-up behavioural questionnaire
- Health outcomes survey (EQ-5D-5L)

Unscheduled visits

Unscheduled visits may occur for reasons including, but not limited to, adverse events, early treatment discontinuation or study termination. In the event of treatment or study termination an unscheduled visit should be performed where possible.

6.2 Study Questionnaires

All participants will complete a behavioural questionnaire, health outcomes survey (EQ-5D-5L) and treatment adherence questionnaire at selected study visits as described below.

Behavioural Questionnaire

The study staff will assist participants to complete this questionnaire. The behavioural questionnaire will collect information on the following:

- Demographics
- HIV and drug treatment history
- Drug and alcohol usage
- Injecting risk behaviors

An abbreviated behavioural questionnaire (follow-up) will be administered at EOT, PTW12 and FU1-6.

Health Outcomes Survey (EQ-5D-5L)

The EQ-5D-5L health questionnaire provides a simple descriptive profile and a single index value for health status. This information can then be translated into a health utility, which can be used for cost-effectiveness analyses.

Adherence Survey

Adherence to glecaprevir/pibrentasvir or sofosbuvir/velpatasvir will be assessed by a four-weekly structured self-report adherence questionnaire.

7. Adverse Events (AEs) and Product Complaints

7.1.1 Adverse Event definition

The medications for this study are supplied via the PBS. Adverse Events and adverse drug reactions will be reported to the Therapeutic Goods Administration as per standard practice for PBS prescribed medications.

7.1.2 Serious Adverse Event (SAE) (including Serious Adverse Drug Reactions)

The medications for this study are supplied via the PBS. Serious Adverse Drug Reactions will be reported to the Therapeutic Goods Administration as per standard practice for PBS prescribed medications.

8. Packaging, labelling, storage and accountability of treatment

The medications for this study are supplied via the PBS. The packaging, labelling and accountability of prescribed treatment will be as per PBS guidelines.

9. Biological samples

9.1 Laboratory supplies and sample processing

Laboratory supplies for collection of research specimens (DBS) will be supplied by the Kirby Institute.

A DBS sample will be collected at the time points specified in the Schedule of Assessments. Samples will be collected by sites, dried (4 hours minimum but preferably overnight) and then posted to the Kirby Institute laboratory within 1 week of collection for storage at -80°C.

DBS samples will be used for study endpoint analysis. HCV RNA will be measured using in-house and commercial assays. Sequencing of the viral genome will also be performed as a more accurate means of genotyping. Data generated from the sequencing may also be used to distinguish relapse from reinfection, to examine the prevalence of mixed infection, to look at clusters and networks in communities and factors associated with relapse including resistance-associated substitutions (RAS) and to perform phylogenetic analyses to examine molecular epidemiology. For HCV phylogenetic analysis, only viral RNA is extracted, amplified and sequenced. No human genomic analysis is being proposed. There is no potential to identify human genetic traits.

9.2 Shipping of biological samples

DBS samples must be posted to the Kirby Institute laboratory once dried (4 hours minimum, but preferably overnight). Each DBS sample card is sealed in a foil zip lock bag which is then sealed in a clear zip lock bag. Samples are posted within 1 week of collection via Express Post.

9.3 HCV RNA Point of Care Testing

A GenExpert machine will be placed within the AHS as part of the study. QA and training will be provided by the KI team. As specified in the Schedule of Assessments, HCV RNA detection will be performed using the Xpert[®] HCV Viral Load Fingerstick point-of-care assay with finger-stick whole-blood samples, as previously validated by our

group (22). A whole-blood sample will be collected from participants via a finger-stick and collected into a 100 μ L minivette collection tube. Immediately after collection, 100 μ L of capillary whole blood will be placed directly into the Xpert[®] HCV Viral Load Fingerstick cartridge (Cepheid, USA; lower limit of quantification of 10 IU/mL) for on-site HCV RNA testing. HCV Viral Load testing of capillary whole blood will be done on a clinic-based GeneXpert R2 6-colour, two module machine operated by a trained nurse as per the manufacturer's instructions. The time to result for this assay is 60 minutes.

9.4 Anti-HCV antibody Point of Care Testing

As specified in the Schedule of Assessment, qualitative anti-HCV antibody testing will be performed using the Alere SD Bioline HCV – a rapid 5-20 minute point-of-care qualitative immunoassay for detection of anti-HCV antibody. A 10 μ L whole blood sample will be collected from participants via a finger stick and added to the round specimen well followed by four drops of the assay diluent. The device provides a visual indicator of the results to display positive, negative or invalid results. As determined by the prescribing physician, point-of-care testing results may be repeated/confirmed with standard laboratory immunoassays via venepuncture.

9.5 HIV 1/2 Antibody Point of Care Testing

At study enrolment, qualitative HIV antibody testing will be performed using the Alere[™] HIV Combo: a point-of-care, 20-minute immunoassay for the qualitative detection HIV-1 p24 antigen (Ag) and antibodies (Ab) to HIV-1 and HIV-2. A 50 µL capillary (whole blood) sample will be collected from the participant and applied to the Sample Pad followed by a Chase Buffer. The device provides a visual indicator of the results to display positive, negative or invalid results. As determined by the prescribing clinician, point-of-care testing results may be repeated/confirmed with standard laboratory immunoassays via venepuncture.

This test is approved by the Australian Government Therapeutic Goods Administration (TGA) and registered as a Medical Device – IVD Class 4 by Inverness Medical Innovations Australia Pty Ltd T/A Alere (Queensland, Australia) and manufactured by Alere Medical Co Ltd (Chiba-ken, Japan).

9.6 HBV Surface Antigen Point of Care Testing

At study enrolment, qualitative hepatitis B surface antigen testing will be performed using the Alere Determine [™] HBsAg – a rapid 15-minute point-of-care in-vitro qualitative immunoassay for detection of hepatitis B surface antigen. A 50 µL whole blood sample will be collected from participants via a finger stick and added to the Alere Determine test pad with the Alere Determine [™] Chase Buffer (Chase Buffer prepared in phosphate buffer). The device provides a visual indicator of the results to display positive, negative or invalid results. As determined by the prescribing physician, point-of-care testing results may be repeated/confirmed with standard laboratory immunoassays via venepuncture. This test is currently not approved by the TGA.

9.7 HCV RNA Recurrence

Among people with an end of treatment response, participants with HCV RNA recurrence (detectable HCV RNA) will be identified. HCV sequencing will be performed from dried blood samples using Core-E2, NS5A or NS5B Sanger sequencing (23). HCV reinfection will be defined by the detection of infection with a strain distinct from the primary infecting strain based on defined genetic distance-based cut-offs and phylogenetic tree construction for reinfection and relapse developed by the investigators (23).

9.8 Future use of biological samples

After the samples have been analysed for the study endpoints as specified in the protocol, remaining samples will be stored for use in future Human Research Ethics Committee approved hepatitis C related research. Additional consent will be sought for permission to store any remaining DBS samples after sample analyses for study endpoints for future hepatitis C related research. As part of the informed consent process and form, participants will indicate their choice using tick boxes to the storage of remaining samples for use in hepatitis C related future research. Samples from participants who indicate they do not wish for their samples to be used in future research, will be destroyed, or returned to participates if indicated, following sample analyses for study endpoints

10. Statistics

Statistical Analyses and Sample Size Calculations

Primary endpoint: The primary endpoint for the HCV treatment as prevention evaluation is HCV prevalence following implementation of the community-based "test and treat" model.

Secondary endpoints include:

- HCV incidence;
- DAA uptake: Proportion with HCV infection initiating DAA therapy;
- DAA treatment outcome: Proportion who initiated DAA therapy and achieved SVR (defined as HCV RNA below the lower limit of quantitation at post treatment week 12);
- DAA treatment completion: Proportion who completed prescribed treatment course;
- Adherence;
- Reinfection incidence post treatment.

The impact of rapid DAA treatment scale-up on HCV incidence and prevalence

Hypothesis: Rapid DAA scale-up will reduce HCV prevalence by >50%

Outcome: Prevalence of HCV infection

Statistical analysis: The proportion of people with current HCV infection (HCV RNA positive) will be calculated by study period. Confidence intervals for proportions will be calculated.

Sample Size: With enrolment of 370 participants (estimated HCV RNA prevalence in Year One, 35%; alpha=0.05; loss to follow up, 30%), the study has 90% power to detect a relative reduction in HCV RNA prevalence of 50% from the initial to the later study period following scale-up of testing and treatment.

Hypothesis: Rapid DAA scale-up will reduce HCV incidence by >50%

Outcome: Incidence of HCV infection

Statistical analysis: HCV incidence will be calculated using person-time of observation. The estimated date of infection will be calculated as the midpoint between the dates of the last undetectable HCV RNA test (or end of treatment) and the first detectable HCV RNA test at the time of HCV infection. Time at risk will commence at the date of first undetectable HCV RNA (or end of treatment), and end at the estimated date of infection, death, loss-to-follow up or end of study. Confidence intervals for rates will be calculated using a Poisson distribution. Poisson regression analysis (or another time-to-event analysis) will be used to estimate crude and adjusted incidence rate ratios (IRR) and corresponding 95% CI to evaluate factors associated with incident infection.

Uptake of DAA therapy among people with HCV infection attending Aboriginal Medical Services

Hypothesis: A community-based "test and treat" intervention integrating point-of-care HCV testing will lead to increased HCV treatment uptake among people attending Aboriginal Medical Services.

Outcome: Treatment uptake (proportion of individuals with HCV infection [HCV RNA positive] initiating DAA therapy)

Statistical analysis: Among people with HCV infection, the proportion of people who initiate DAA therapy will be calculated. Factors associated with DAA uptake will be assessed by logistic regression analyses. Sample Size: Given the assumed population distribution, we will enrol 120 participants with prevalent chronic HCV infection and 29 with incident HCV infection (with spontaneous clearance in 25% of incident cases). As such, 142 will be considered for DAA therapy. Assuming DAA uptake of 70% (based on LiveRLife [unpublished data]), the 95% Cl around this estimate is 62-78%. We will have 80% power to detect an odds ratio of 2.66 or greater (alpha=0.05) for a variable that is 50% prevalent (i.e. recent injecting drug use).

Response to DAA therapy among people with chronic HCV infection

Hypothesis: A community-based "test and treat" intervention integrating point-of-care HCV testing among people attending Aboriginal Medical Services will lead to HCV treatment response of >90%.

Outcome: Treatment response (SVR, defined as HCV RNA below the lower limit of quantitation 12 weeks following end of treatment).

Statistical analysis: The proportion of people achieving SVR12 will be calculated with corresponding 95% CI. Factors associated with treatment response will be assessed by logistic regression analyses.

The proportion completing the prescribed treatment course will be calculated with corresponding 95%CI. Factors associated with treatment completion will be assess by logistic regression analysis.

Estimate incidence of HCV reinfection after successful DAA therapy

Hypothesis: HCV reinfection following treatment will be associated with ongoing high-risk behaviours facilitating transmission.

Outcome: Incidence of HCV reinfection following DAA therapy

Statistical analysis: Rates of HCV reinfection following treatment will be calculated using person-time of observation, with the methodology described in Aim 1, except that time at risk will commence at the date of end of treatment. Poisson regression analysis (or another time-to-event analysis) will be used to estimate crude and adjusted IRRs and corresponding 95% CI to evaluate factors associated with reinfection.

11. Data Safety and Monitoring Board (DSMB)

A Data Safety Monitoring Board will not be used for this study as treatment is being prescribed and supplied according to PBS indications.

12. Data collection, source documents and record retention

The Principal Investigator and the institution where the study will be conducted will permit study-related monitoring, audits, ethics committee review and regulatory inspection providing direct access to source documents.

Data will be collected on study specific electronic or paper copy case record forms. The Principal Investigator is responsible for ensuring the data collected are complete, accurate and recorded in a timely manner.

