PARTICIPANTS WITH OR AT RISK OF HCV							
POC HCV RNA (Finger-stick)	Х	х	х	х	х	х	х
Dried blood spot collection (Finger-stick)	Х	х	х	х	х	х	х
Clinical assessment	Х						
Behavioural questionnaire	Х						
Follow-up behavioural questionnaire		Х	х	Х	Х	х	х
Health outcomes survey (EQ-5D-5L)	Х	Х	X	Х	Х	Х	Х
POC HIV serology (HIV antibody)	Х						
POC HBV serology (Hepatitis B surface antigen)	Х						

Schedule of assessments B: Treatment – For participants with HCV infection

Assessment / Procedure	On and Post-Treatment Phase ^a				
Study visit	Baseline ^b	Week 4	Week 8 د	EOT	PT W12
Study weeks	0	4	8	8 or 12	20 or 24
Visit Window (Days)	-	+/-7	+/-7	+/-7	+/-7
PARTICIPANTS COMMENCING DAA TREATMENT					
POC HCV RNA (Finger-stick)	Х			х	Х
Dried blood spot collection (Finger-stick)	Х			Х	Х
Clinical assessment	Х	Х	Xc	Х	Х
Follow-up behavioural questionnaire				Х	Х
Health outcomes survey (EQ-5D-5L)				Х	Х
Treatment adherence		Х	Xc	Х	
HCV genotype (Local laboratory)	Х				
Quantitative HCV RNA (Local laboratory)	Х				
Liver Function Tests/Full Blood Count/Biochemistry	Х				
Pregnancy test	Xd				
Study drug dispensing	X	Х	Xc		

Кеу

a On and post treatment visits can be conducted concurrently with Follow Up visits if appropriate

b Screening and baseline (treatment initiation) can (and should, if possible) occur on the same day

c For participants receiving 12 weeks sofosbuvir/velpatasvir only

d Women of child bearing potential only

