4.2 Visit Schedule

All participants will complete a screening visit as outlined below and in the Schedule of Assessments.

Those participants who are HCV RNA positive will be offered DAA therapy. Participants who decide to initiate DAA treatment will have on-treatment and post-treatment assessments as outlined in the Schedule of Assessments and described in Section 6.0. The treatment regimen of eight weeks glecaprevir/pibrentasvir or 12 weeks sofosbuvir/velpatasvir will be prescribed via the PBS S85. Participants who are HCV RNA positive may commence DAA treatment at any time during the study.

Following enrolment into the SCALE-C Cohort, regardless of HCV RNA or DAA treatment initiation, a followup visit will be conducted every 6 months for the duration of the study (up to three years; FU1–FU6).

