Appendix 1: Examples of other studies

HCV testing, diagnosis and assessment of HCV-related liver disease - the LiveRLife Project

On-site HCV testing with integrated care improves linkage to HCV care and treatment among PWID (24). In 2014-2017, the LiveRLife project piloted an intervention using a liver health promotion campaign, non-invasive liver fibrosis assessment (transient elastrography; Fibroscan^{*}), dried-blood spot testing, and point-of-care HCV RNA testing (GeneXpert, Cepheid) among PWID attending 13 sites in NSW, Queensland, and South Australia (seven drug treatment clinics, one Aboriginal community-based primary health clinic, the Sydney Medically Supervised Injecting Centre, one homelessness service, and one needle and syringe program site) (25).

This project:

- Evaluated knowledge/attitudes about liver disease and used social marketing methods to develop evidence-based messaging to enhance liver disease assessment;
- Developed LiveRLife resources through extensive focus group testing (posters, 16-page educational booklet, Fibroscan[®] results card, LiveRLife website, and educational film);
- Established a cohort study of PWID. Each clinic had four campaign days over four weeks. Participants completed a survey, Fibroscan[®] assessment, nurse assessment and finger-stick HCV RNA testing, with 60% returning for clinical follow-up 2-12 weeks post-intervention (26);
- Performed the first international evaluation of point-of-care finger-stick HCV RNA test (27, 28).

Among Aboriginal people enrolled, the majority reported a history of IDU (ever 97%, current 75%) and incarceration (75%), and HCV RNA prevalence was 45%, with prior anti-HCV Ab antibody and HCV RNA testing were reported by 64% and 60%, respectively (unpublished data). There was high acceptability (87%) of transient elastography. Of note, among those with detectable HCV RNA, 74% were willing to commence HCV treatment. These data support use of this model in a larger prospective study to evaluate whether this intervention can increase HCV testing, access to care and treatment, and reduce risk behaviours associated with transmission among Aboriginal people attending culturally-appropriate community primary healthcare facilities.

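### SVR is tied to a single test at post-treatment week 12 among all DAA starters, so later scheduled HCV RNA results cannot count

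*Protocol*

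**What the plan says.** Section 10 (Statistics) lists the DAA treatment outcome as "Proportion who initiated DAA therapy and achieved SVR (defined as HCV RNA below the lower limit of quantitation at post treatment week 12". This sets both the denominator (those who started) and the one result that qualifies. The subsection on response to DAA therapy repeats the timing: "Treatment response (SVR, defined as HCV RNA below the lower limit of quantitation 12 weeks following end of treatment". The abbreviations list defines SVR12 in the same way. The planned analysis is brief: "The proportion of people achieving SVR12 will be calculated with corresponding 95% CI", followed by logistic regression for factors associated with response. The hypothesis is that the intervention "among people attending Aboriginal Medical Services will lead to HCV treatment response of" at least 90%. A secondary objective (Section 2.3) is to assess factors associated with failing to reach SVR.

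The visit plan supplies further RNA results. Section 4.2 says that after enrolment, "regardless of HCV RNA or DAA treatment initiation, a followup visit will be conducted every 6 months for the duration of the study". Section 6.1 and Schedule of Assessments A place a point-of-care HCV RNA test and a dried blood spot at each of these visits, FU1 to FU6. A note to Schedule B allows post-treatment visits to be held together with follow-up visits. Section 9.7 plans sequencing to separate reinfection from relapse. No section says that an RNA result from a later follow-up visit may establish SVR.

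**The concern.** The endpoint asks whether treatment cured the infection, but as worded it also asks whether the participant was tested at one particular visit. Someone who misses PTW12 stays in the denominator and has no route into the numerator, even if a scheduled test some weeks or months later is undetectable.

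Two things are at stake. First, the observed proportion could fall short of the hypothesised 90% because of attendance and not because treatment failed. Second, the regression on failure to achieve SVR would mix virological failures with people who were cured but not tested, so its associations would partly be those of missed visits.

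**Working it through.** **Inputs from the protocol**
- Cure rate: above 95% (synopsis and Section 1.0). I use 95%, with 97%, 99% and 100% as sensitivity values.
- People considered for DAA: 120 prevalent + 0.75 × 29 incident = 141.75, stated as 142 (Section 10).
- Uptake: 70% (Section 10), so 0.70 × 142 ≈ 99 starters.
- Hypothesised response: at least 90%.

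**Reproducing the plan's own figure.** The protocol gives no precision or power for SVR. The nearest stated figure is the interval for uptake: 0.70 ± 1.96 × √(0.70 × 0.30 / 142) gives 62.5% to 77.5%, which agrees with the stated 62–78%.

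**Assumption.** The share *m* of starters without a PTW12 result is not given, so it is varied. Missing is taken to be unrelated to cure.

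**Step 1: proportion under the literal wording.** SVR among all starters = cure × (1 − *m*). The last column is the binomial chance of observing at least 90% (90 or more of 99).

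| *m* | SVR at 95% cure | P(observed ≥ 90%) |
|---|---|---|
| 0% | 95.0% | 0.97 |
| 5% | 90.3% | 0.50 |
| 10% | 85.5% | 0.08 |
| 20% | 76.0% | <0.001 |
| 30% | 66.5% | <0.001 |

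**Step 2: break-even.** The expected proportion is 90% when *m* = 1 − 0.90/cure. This gives 5.3% at 95% cure, 7.2% at 97%, 9.1% at 99% and 10% at 100%.

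**Step 3: who the non-SVR cases are.** Take 100 starters, 95% cure and 20% missing. SVR is 76, so non-SVR is 24. Of these, 0.95 × 20 = 19 are cured but untested, 1 is uncured and untested, and 0.05 × 80 = 4 are observed failures. At 10% missing, 9.5 of 14.5 non-SVR cases are cured but untested.

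**Step 4: what later tests could recover.** If a share *r* of those who missed PTW12 has a later RNA result, SVR = 0.95 × (1 − *m* × (1 − *r*)).

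| *m* | *r* = 50% | *r* = 75% | *r* = 90% | *r* needed for 90% |
|---|---|---|---|---|
| 10% | 90.3% | 92.6% | 94.1% | 47% |
| 20% | 85.5% | 90.3% | 93.1% | 74% |
| 30% | 80.8% | 87.9% | 92.2% | 82% |

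The protocol gives no value for *r*.

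**Step 5: timing, for a same-day start.** On the 8-week course PTW12 falls at week 20 and FU1 at week 24, so FU1 is 16 weeks after treatment. On the 12-week course PTW12 and FU1 both fall at week 24, and the next scheduled test is FU2 at week 48.

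**The case against.** The strongest objection is that handling of missing results usually belongs in the SAP, which is not shown, and that no sentence in the protocol says a missing PTW12 result is a failure. That is correct: the classification follows from the literal endpoint and is not a written rule. What stands is that the protocol itself fixes the denominator and the single qualifying time point, and that definition leaves no place for a later result.

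A second objection is that all starters is a legitimate denominator, since the hypothesis concerns what the intervention achieves and retention is part of that. I accept this; the all-starter figure should stay. It does not explain why an undetectable result at a later scheduled visit should be disregarded.

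A third is that later tests let reinfection into a cure endpoint. Section 1.0 cites an incidence of 31 per 100 person-years in Aboriginal PWID, so this matters for late positives. It does not affect a late undetectable result.

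A reader might infer more than the documents support:
- *That only tests within ±7 days count.* The ±7 days is a visit window in Schedule B; nothing makes it an analysis window.
- *That the 90% hypothesis must fail.* This depends on attendance at PTW12, which is not given. The 30% loss to follow-up is a cohort assumption between study periods. The pilot figure in Appendix 1, "with 60% returning for clinical follow-up 2-12 weeks post-intervention", concerns a different visit, not a post-treatment visit after DAA therapy.
- *That later tests would settle most missed cases.* People fully lost also miss the follow-up visits, and no recovery share is given.
- *That 90% should be judged by the confidence limit.* The protocol attaches no test to it. With 99 starters all tested and true cure of 95%, the exact lower limit reaches 90% only with 96 or more cured, a chance of about 0.26. Such a criterion would be a new and demanding rule.

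**Conclusion.** The point holds as a defect in the endpoint definition: scheduled RNA results that bear directly on cure cannot count towards SVR. At 95% cure, more than about 5% of starters without a PTW12 result puts the expected all-starter proportion below 90%; at perfect cure the limit is 10%. At 95% cure and 20% missing, about 19 of every 24 non-SVR cases would be cured people who were not tested, and the failure-factor model would reflect that.

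These figures rest on the literal reading of the definition, on missingness unrelated to cure, and on an assumed missing share. They show how sensitive the endpoint is; they do not predict that the hypothesis will fail. This is a secondary endpoint, so the change is worth making but does not touch the primary analysis.

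**What to change.** 1. Define SVR as HCV RNA below the lower limit of quantitation at the first available test 12 or more weeks after end of treatment, whether at PTW12 or a later follow-up visit.
2. Classify a late positive as relapse or reinfection by the sequencing in Section 9.7, and state how a late positive that cannot be sequenced is handled.
3. Report SVR among all starters (no result counted as not achieved, and stated as such) and among those with a result. State how many results came from PTW12 and how many from later visits.
4. Fit the model for factors associated with failure to achieve SVR in those with a result.

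The cost is wording in the protocol or SAP; the visits, RNA tests, blood spots and sequencing are already planned. There are two limits. Late positives depend on successful sequencing from dried blood spots, and people fully lost to follow-up are not recovered, so the all-starter figure will still carry some missingness.
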